### **III. RESEARCH APPROACH**

#### **A. Overview and Design**

The small randomized controlled trial of an intensive curriculum and school garden intervention will be implemented in elementary schools in two communities (Shiprock and Tsaile). The study will begin in year 1 with a period of engagement and recruitment of schools in each community; with the goal of recruiting three schools *in each community* to start the run-in phase (see Figure 1). The run-in period will include time for greater engagement with the school community, an assessment of the potential garden site and an assessment of evaluation readiness. Depending on whether all three schools in the community qualify for the study at the end of run-in, or only two schools per community, we will randomize three or two schools to intervention or delayed intervention status in each community. We will have either two intervention schools and 4 delayed intervention schools, or 2 intervention schools and 2 delayed intervention schools, depending on the run-in information. We will conduct baseline data collection (T1) at the beginning of the school year in Year 2

[figure not shown]
with both children and parents. Students in the intervention group will receive the curriculum and school garden during that academic school year. At the end of the school year, we will conduct the T2 assessment in children and parents. The main evaluation period is between T1 and T2, and the statistical analysis methods refer to the T2 versus T1 change in outcome measures (healthy eating and gardening). After that, at the beginning of the next school year (Year 3), the delayed intervention schools will receive the intervention. During Year 3, we will also conduct quarterly community gardening workshops for adult family members in all schools.

Attendance at these will be tracked. A final assessment (T3) will be conducted at the end of the second school year in all the randomized schools to describe behaviors in children and parents over time, using a quasi-experimental design that estimates change in the delayed intervention group between T2 and T3, attributable in part to the delayed intervention.

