## D. School Engagement and Recruitment

Our first aim is to engage and recruit elementary schools from two communities on the Navajo Nation for the randomized control trial of the Yéego! Healthy Eating & Gardening intervention. We recognize that personal interactions with key stakeholders is an essential part of community engagement. This will require the assistance of “key influential” in the school system, faculty educators at Diné College, and local residents who are Navajo members of our research team. Based on our previous experience in recruiting of organizations for group-randomized trials, we plan to implement the following steps to recruit and engage potential schools as research partners. In defining the population of schools from which to recruit, we note there are about 90 elementary schools in the Navajo Division of Education system, including 16 in Shiprock and 11 in Tsaile. We will identify schools in Tsaile and Shiprock who meet the eligibility criteria for the study. The eligibility criteria will include having been in existence for at least three years, school size (have between 40 to 100 students in grades 3 and 4 combined), have more than two-thirds Navajo students and satisfy a garden site checklist that can overcome garden barriers (e.g. have access to water) (Figure 2). Information about potential schools will come from the initial phone screening and a school questionnaire. Each school will be contacted by phone and letter to assess their initial interest in participating in the study. After initial conversations, study staff will arrange a meeting with school faculty meeting to discuss the intervention and study procedures in detail. The meeting will provide detailed information on the student recruitment and data collection process and emphasize efforts to minimize disruption of daily classroom routine. For interested schools, we will also do an initial assessment of the school resources and garden site. From these meetings we hope to identify at least six schools, three in each community for further engagement. Our next phase with the schools will serve as a “run-in” period to the trial. During this time we will hold meetings with teachers and parents, and conduct initial surveys to gauge their level of interest, ability to engage in the types of evaluations used in the main study, and likelihood of engaging fully in the curriculum and school garden intervention. Our goal is to randomize a minimum of four schools (two in each community) that will participate for the duration of the project. If all schools qualify for the study on completion of run-in, we will randomize all six schools, two to intervention and four to delayed intervention.

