## Student Follow-up Assessment (amended due to COVID-19)

### Preparation

Yéego! Healthy Eating & Gardening project has mailing addresses (including PO Box numbers) for almost all of the 3rd and 4th grade students in all six schools. For those students for whom the study has no address, contact will be made via phone and email requesting mailing address. It is anticipated that we will obtain mailing addresses that will reach ALL the 3rd and 4th grade students.

In addition to the mailed survey, parents/guardians that provided email addresses will be sent an email with a secure link to the follow-up survey. The weblink will send participants to a new virtual server with more restrictive access. The Yeego Server and the process to protect the files stored locally at Fred Hutch was approved by Information Security Office and IRB 08-12-2019.

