## E. Analysis Plan

Two of our four primary outcome measures in children (tendency to choose fruit and vegetables to eat during snacks/meals and gardening self-efficacy) will be measured through questions that use a Likert-type scale with four response options. With numeric codes assigned to each response option, means and standard deviations will be calculated per question and overall. Thus, possible mean values range from one to four. The intention to treat analysis will be a t-test comparing the change in mean values from baseline (beginning of school year at T1) to follow-up (end of school year at T2) in the intervention schools to those changes in mean values in the schools receiving the delayed intervention. This differential change in groups between T1 and T2 is the estimated intervention effect. The estimated effect of the intervention will also be analyzed using linear mixed models with T2 individual outcome as the dependent variable and intervention assignment as the

independent variable, adjusting for T1 individual outcome and school random effect. It will also allow for adjustment for additional covariates (school within intervention group if applicable) and for known or probable individual level confounders. Information from all responding students will be included in the analysis, with adjustment for repeated measures (expected to be the majority of the students). This will assess robustness of inferences from the simpler model. A sensitivity analysis without adjusting for possible intra-school correlations will be performed using linear regression models. In addition, the Akaike Information Criterion will be compared between the simpler model and the theoretically correct multilevel model to check model fit.

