## V. Protection of Human Subjects

### A. Risks to Human Subjects

**Human Subjects Involvement, Characteristics, and Design.** The primary study population is children, both male and female, in grades 3 or 4. One member of their adult family (21 years or older) is included in the secondary study population. Because of the multicomponent nature of the intervention, including the school garden, and parent workshops, participation in the intervention activities will include children in other elementary grades and other parents. The proposed study will take place in elementary schools within the Shiprock, NM and Tsaile, AZ area; both rural areas located within the Navajo Nation. The majority of the

participants in the study will be American Indian (AI), primarily members of the Navajo Nation. It is anticipated that as many as 960 participants will be formally enrolled in the study: 80 3rd and 4th grade students within each of 6 distinct schools (three in Shiprock, 3 in Tsaile), plus one parent/caregiver for each child. Participants will be recruited through the enrolled, participating elementary schools selected.

**Study Procedures, Materials, and Potential Risks.** Schools will be recruited to the study and will take part in a “run-in” including planning with the study, and an evaluation of readiness to complete study surveys. We will recruit from 6 elementary schools in two communities (two schools in Shiprock, NM and three schools in Tsaile, AZ). We will recruit and enroll children in grades 3 and 4 (ages 8-11) who attend the selected elementary schools participating in the proposed study.

Data will be collected for research purposes only. Materials to be obtained include interviewer-administered questionnaires and anthropometric measures (height and weight) at three time points of the proposed study; at the beginning-T1 (August) and end-T2 (June) of the intervention school year and the end of the second school year-T3, once the delayed intervention has completed the intervention. We will assess process evaluation measures including recruitment, retention and intervention fidelity.

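### Does the optional school-within-group covariate, or the lack of a community term, undermine the supporting mixed model?

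*Combined protocol and SAP*

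**What the plan says.** In section IV.E (Analysis Plan) the main test for the two Likert-type primary outcomes is a t-test on change from T1 to T2. A linear mixed model follows, with the T2 score as dependent variable and arm as independent variable, "adjusting for T1 individual outcome and school random effect". The next sentence reads: "It will also allow for adjustment for additional covariates (school within intervention group if applicable"; it also allows for individual-level confounders, which it does not name. The purpose of the model is then given: "This will assess robustness of inferences from the simpler model". A regression that ignores correlation within schools is listed as a sensitivity analysis, and "the Akaike Information Criterion will be compared between the simpler model and the theoretically correct multilevel model to check model fit".

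The healthy eating score is assigned a t-test and home gardening a z-test later in the same section. Neither contains the covariate.

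On the design, section III.A says "we will randomize three or two schools to intervention or delayed intervention status in each community", and section III.D says that if all qualify "we will randomize all six schools, two to intervention and four to delayed intervention". The amended follow-up procedure speaks of "grade students in all six schools". Section V.A counts "6 distinct schools (three in Shiprock, 3 in Tsaile", while its following paragraph gives two schools in Shiprock and three in Tsaile and still calls the total six.

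**The concern.** Schools are nested in arms, so a set of school indicators already determines which arm a child is in. If the optional covariate were entered as fixed, the arm effect could not be separated from it. The between-school variance, against which arm has to be judged, could not be estimated either. The model meant to check the simpler test would then fail or, worse, print an arm coefficient with too small a standard error.

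The second worry is that randomisation is carried out within two communities, and the analysis does not name community. If one-year change differs between Shiprock and Tsaile, that difference goes into the error term.

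**Working it through.** **Plan's own figure.** Section V.A anticipates 960 participants: 80 students × 6 schools × 2 (child and adult) = 960. It reproduces, and it agrees with three schools per community. The plan gives no ICC, power or detectable effect.

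**Inputs.**
- From the documents: two communities; 2 v 4 or 2 v 2 schools; SD 0.48 for the fruit and vegetable choice score (section IV.C).
- Illustrative cluster size: 48, from the 60% recruitment goal in section IV.B applied to 80 students.
- Assumed: T1–T2 correlation 0.5; ICC 0.01 to 0.05; one intervention school per community, inferred from sections III.A and III.D.

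**1. Random reading.** Every school is in exactly one arm, so school within arm has the same levels as school (4 or 6) and gives the same random-effect covariance matrix. The term duplicates what is there. Deleting it changes no estimate.

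**2. Fixed reading.** With six schools the columns are intercept, T1, arm and 5 school indicators: 8 columns, rank 7. With four schools they are 6 columns, rank 5. The arm coefficient is not estimable in either layout.

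If software drops one reference school per arm, the printed arm coefficient is one intervention school minus one delayed school. Its SD relative to the two-against-four contrast is √2 / √(1/2 + 1/4) = 1.63.

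A contrast of averaged school means can still be formed. Either contrast, judged on within-school error alone, has its variance understated by the factor 1 + ICC × m/(1 − ICC), and its true two-sided error is 2[1 − Φ(1.96/√factor)]. For m = 48:

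| ICC | Factor | 1.96/√factor | Type I error |
|---|---|---|---|
| 0.01 | 1.485 | 1.608 | 10.8% |
| 0.02 | 1.980 | 1.393 | 16.4% |
| 0.05 | 3.526 | 1.044 | 29.7% |

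If all 80 per school in section V.A took part, the factors would be 1.808, 2.633 and 5.211, and the errors 14.5%, 22.7% and 39.1%.

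**3. Which reading the text supports.** The school effect has just been declared random. The model is called multilevel and set against a regression without within-school correlation. Section II (Specific Aims) promises adjustment for clustering by school. Section IV.C refers to a single intervention school and to one or more delayed schools, so a nested term that applies only when an arm has several schools gives the qualifier a natural meaning. The fixed reading needs school to be both random and fixed in one model.

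**4. Community, six schools.** Arm plus community is full rank (4 columns with intercept and T1). With the same arm ratio in both communities, omission leaves the arm estimate essentially unchanged and only its estimated error moves. In units of the school-mean SD, a community difference d multiplies the residual variance by 1 + 0.375d²: 1.38 at d = 1 and 2.5 at d = 2. In a school-level test, type I error then falls from 5% to 2.9% and 0.6%, which is conservative.

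Adding community takes df from 4 to 3 and critical t from 2.776 to 3.182, a ratio of 1.15. With four schools df go from 2 to 1 and critical t from 4.303 to 12.706.

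The T1-adjusted residual SD is 0.48 × √(1 − 0.25) = 0.416. At ICC 0.02 the school-mean SD is 0.416 × √(0.02 + 0.98/48) = 0.0836. Simulated power of the mixed model (REML, 8,000 runs per cell, equal school sizes):

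| Effect | Community difference | Without | With |
|---|---|---|---|
| 2.5 SD (0.21 points) | 0 | 56.9% | 45.8% |
| 4 SD (0.33 points) | 0 | 92.6% | 85.5% |
| 2.5 SD | 1.155 SD (0.10 points) | 41.5% | 45.8% |
| 4 SD | 1.155 SD (0.10 points) | 83.1% | 85.5% |

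With no community difference the interval half-width goes from 0.198 to 0.228 points, and the type I error, already low at 2.1%, falls to 1.0%. With 24 to 60 children per school the gains at 1.155 SD are 1.8 points (38.1% to 39.9%) and 1.4 points (79.6% to 81.0%). Break-even is near 0.95 to 1.00 SD with equal sizes and 1.06 SD with unequal sizes, which is 0.08 to 0.09 points.

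**The case for a change.** The strongest case for a change is that the words lean towards the harmful reading. The term is listed as an extra covariate, after the random effect and beside individual confounders. Every layout has at least two schools per arm, so the qualifier would always be met. The error it invites is anti-conservative, and it would fall on the only comparison of primary outcomes in section IV.E that expressly models clustering by school. Deleting the phrase costs nothing.

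The ambiguity is real, and so is the algebra. What does not stand is the step from there to a defect. The plan permits the adjustment without committing to it. The harm needs a fixed term, an unremarked rank deficiency and a school variance set to zero, all in an optional extension of a supporting model that section IV.E introduces for two of the four primary outcomes. An analyst who tried it would normally see the aliased term and return to the base model, which is sound.

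For community, the argument that analysis should follow the randomisation is a fair principle. With four school-level df it has a price, and the plan gives no data on whether the two communities change differently. The power comparison rests on one correlation and mainly one ICC. At the same standardised difference of 1.155 SD and an effect of 2.5 SD, the gain is about 2 points at ICC 0.01 and 7 at ICC 0.05, so 1 to 4 points is not a full sensitivity range.

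**Conclusion.** No change is needed. The parenthesis is either a redundant name for the random school effect, with no effect on any result, or a fixed term that cannot be fitted alongside arm. Analysts would settle this sensibly by keeping school random only, as the plan already states. The inflated errors of 11% to 30% at 48 children per school (up to 39% at 80) belong to the fixed reading and to assumed ICCs. The rank result needs no such assumption.

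Leaving community unnamed is a fair trade-off. With balanced allocation it does not bias the arm estimate, and at worst it makes a school-level test conservative. With six schools, adding it loses 7 to 11 points of power and widens intervals by 15% if the communities do not differ. It gains 1 to 4 points at an assumed difference of about 0.10 points, and it would leave a single df with four schools. The existing wording already leaves room for it.

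The two school counts in section V.A are a clerical slip: two plus three is five, while the same sentence, the 960 total and the follow-up text all rest on six.

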The picture sort method uses references to 26 commonly consumed food items by Navajo chosen to represent six of the broad food components captured within the AHEI, and four other Navajo food groups. Frequency of consuming foods from each group, with specific focus on the six AHEI relevant components will be estimated and compared across schools. The healthy components are fruits, vegetables, whole grains, and nuts and legumes, and the so-called “unhealthy” components based on AHEI scoring are sugar-sweetened beverages and fruit juice, and red/processed meat. Differential change in the derived healthy eating score will be estimated, and evaluated using a t-test, conservatively, assuming a Normal distribution for the score, based on the Central Limit Theorem. Similarly, the proportion of children who participate in gardening at home will be calculated for each school, and the differential change estimated and evaluated using a z-test for proportions.

Secondary outcomes, including those collected from the parents of participating children, will be analyzed similarly. Mean values and standard deviations for scored variables will be calculated, and intervention effects estimated, and evaluated using t-tests. Frequencies will be estimated for categorical outcomes and intervention associated differences in frequency distributions across categories will be evaluated using Pearson's Chi-square test. Since both parent and child data will be collected, parent-child pairs will be created and explored, including the use of generalized mixed models to account for within-family correlations. The form of dyad analysis used will take into account that the members of the dyad are distinguishable.

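### The robustness model in section IV.E does not match its stated analysis set, and the z-test for gardening at home is given neither a within-child variance nor a school term

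*Combined protocol and SAP*

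**What the plan says.** Section IV.E opens with "Two of our four primary outcome measures in children", the two Likert-type scores. For these, "The intention to treat analysis will be a t-test comparing the change in mean values from baseline" to follow-up, intervention against delayed schools. A second analysis uses "linear mixed models with T2 individual outcome as the dependent variable", "adjusting for T1 individual outcome and school random effect". Its stated purpose is: "This will assess robustness of inferences from the simpler model". The same paragraph adds: "Information from all responding students will be included in the analysis, with adjustment for repeated measures (expected to be the majority of the students".

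The other two primary outcomes come later in IV.E. For the picture-sort score: "Differential change in the derived healthy eating score will be estimated, and evaluated using a t-test". For gardening at home, a proportion is calculated for each school and "the differential change estimated and evaluated using a z-test for proportions". No mixed model is named for either.

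Three other places bear on this:

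- The Specific Aims (section II) list gardening at home among the primary outcomes and say that the effect analyses will account for school-level clustering.
- Section IV.C defines gardening at home as the proportion who garden there at least sometimes.
- Section IV.B follows the children surveyed at baseline (Follow-up Assessment Notification; Follow-up survey delivery). It also lets later arrivals join on request (New Student Enrollment) and treats full T2 response as a goal.

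**The concern.** There are two separate gaps.

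1. **Analysis set of the robustness model.** A child without T1 has no covariate value, and a child without T2 has no outcome value. Both kinds of child are foreseen in IV.B, yet IV.E says that all responders are included and names no imputation or missing-baseline rule. An analyst cannot follow both statements and would have to choose after seeing the data.
2. **Variance of a primary test.** The same children are measured twice, and whole schools are randomised. A textbook z-test for proportions allows for neither. For gardening at home there is no second model to fall back on, so the standard error of one of four primary results is left open.

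**Working it through.** The plan gives no ICC, T1-T2 correlation, retention rate or power figure for these analyses, so there is no planned figure to reproduce. Quantities marked *assumed* below are illustrations.

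**Part 1: who enters the T2-on-T1 model**

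| | T1 | T2 | Row in the model? |
|---|---|---|---|
| Both waves | yes | yes | yes, one row |
| T1 only | yes | no | no (outcome missing) |
| T2 only | no | yes | no (covariate missing) |

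Section V.A anticipates 6 × 80 = 480 children. At *assumed* T2 non-response of 10%, 20%, 30% and 40%, the model keeps 432, 384, 336 and 288 of them, and no T2-only child at any rate. With one row per child there is no within-child covariance left to estimate.

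**Part 2: the z-test for gardening at home**

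Inputs:

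- Allocation: 2 intervention and 4 delayed schools (III.D, six-school case).
- Children per school: the 60% enrolment goal (IV.B) × 40 to 100 pupils (III.D) = 24 to 60, midpoint m = 42. Arms are 84 and 168. Section V.A gives 80 as an upper plan.
- *Assumed*: proportion 0.5, correlation r = 0.3 to 0.7, ICC of change 0 to 0.05, two-sided 5% test.

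Formulae:

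- z-test, waves taken as independent: SE = √[2 × 0.25 × (1/84 + 1/168)] = 9.4 points.
- Paired, no clustering: 9.45 × √(1 − r) = 9.45 × √0.5 = 6.7 points at r = 0.5.
- Paired and clustered: multiply by √DE, where DE = 1 + (m − 1) × ICC. At ICC 0.05, DE = 1 + 41 × 0.05 = 3.05 and SE = 6.68 × √3.05 = 11.7 points.
- Large-sample false-positive rate = 2 × [1 − Φ(1.96 × SE used / true SE)]. For the z-test, SE used / true SE = 1/√[(1 − r) × DE]. The proportion and the number of schools cancel.

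Results at r = 0.5, m = 42:

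| ICC | DE | True SE (points) | False positives, z-test |
|---|---|---|---|
| 0 | 1.00 | 6.7 | 0.6% |
| 0.01 | 1.41 | 7.9 | 2.0% |
| 0.02 | 1.82 | 9.0 | 4.0% |
| 0.05 | 3.05 | 11.7 | 11% |

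At ICC 0.05 the rate runs from 18% (r = 0.3) to 4% (r = 0.7). With 80 children per school and r = 0.5 it runs from 4% (ICC 0.01) to 21% (ICC 0.05).

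The two errors cancel when (1 − r) × DE = 1. At r = 0.5 and m = 42 that is ICC = 1/41 = 0.024; below it the test is conservative, above it too liberal.

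Correcting pairing alone leaves SE used / true SE = 1/√3.05 at ICC 0.05, and the false-positive rate becomes 26%. The two corrections must therefore be made together.

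**Part 3: the reference distribution**

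Suppose a correct school-level statistic is compared with 1.96 when it follows t on (schools − 2) df. The false-positive rate is P(|t| > 1.96) = 12% on 4 df (2 v 4 schools) and 19% on 2 df (2 v 2). Adding a school effect with a normal reference would thus not restore the 5% level.

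**The case against.** - **The robustness model works.** A reader might infer that it cannot be fitted, or that the main analysis fails with it. Neither follows. The T2-on-T1 model runs on children with both waves, and conditioning on T1 is one legitimate use of the repeated measure. The intention-to-treat t-test does not depend on the sentence at issue. The remark that repeated measures apply to most students also shows that the authors expected one-wave children. What stands is that those children are said to be included and no method includes them.
- **Independence is not stated.** A reader might infer that the plan treats T1 and T2 as independent samples. Section IV.E gives no variance formula, and a z-test with a paired variance is not ruled out. The Specific Aims also promise adjustment for clustering. This is an omission, not a stated error, but for a primary test it still has to be filled.
- **Ignoring pairing alone is conservative.** This is correct: 0.6% at r = 0.5 with no clustering. Any excess of false positives comes from clustering.
- **The mixed model may be meant for all four outcomes.** This is possible, but it is introduced under the two Likert scores, and a linear model is not an obvious choice for a yes/no outcome.
- **Loss at T2.** After the move to online, mail and phone follow-up, a reader might infer serious bias from unequal loss. Under assumed loss of 20% v 30%, a simulation put the bias at 0.02 to 0.03 SD, with opposite signs for the unpaired and change-score analyses. That is too small to be a main reason for change.
- **Substitute adults.** A reader might extend the point to parents replaced at follow-up. That touches secondary outcomes only. Excluding all of them would rely on an interviewer's note that online or mail completion may not produce.

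**Conclusion.** The point holds in two limited parts. First, the robustness model and the sentence on all responding students do not match, and children seen at one wave have no stated place. This needs no assumed figures. Second, the only test named for gardening at home leaves both the within-child variance and the school term unspecified, despite the commitment on clustering in the Specific Aims. A standard z-test would misstate the standard error, but the documents do not support saying in which direction. Over the ranges tried with 42 children per school and r = 0.5, false positives run from 0.6% to 11% and are near nominal at an ICC of about 0.02. These rates rest on assumed correlation and ICC, equal school sizes and a large-sample approximation. The assumed 50% proportion affects only the standard errors in points. Confidence is medium. The change is worth making before analysis but does not call the design into question.

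**What to change.** 1. **Gardening at home.** Replace the z-test with a T1-adjusted analysis in children with both waves, kept in their randomised school, that includes the school effect and is reported in percentage points.
2. **Healthy eating score.** Name the same T1-adjusted, school-clustered analysis.
3. **Small-sample inference.** With 4 to 6 schools, do not use a normal reference. One workable form adjusts each child's T2 value for T1, averages within school, and compares the school means with t on the number of schools minus 2 (4 df for 2 v 4, 2 df for 2 v 2).
4. **Robustness model.** State that the T2-on-T1 model is a both-wave analysis, valid if data are missing at random given T1, and delete the sentence on all responding students and repeated measures. Alternatively, name a separate sensitivity model on T1 and T2 rows with arm-by-time, child and school-by-time terms, in which one-wave children enter. The school-by-time term is needed because a school intercept alone cancels out of the change. Such a model may be hard to fit with six or fewer schools, so state a fallback.

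Cost: SAP wording and modest programming, with no new data, since section IV.D already logs completion of each assessment. One-wave children leave the main T1-adjusted analysis. Intervals widen: for a paired SE of 11.7 points, the 95% half-width is 1.96 × 11.67 = 22.9 points with a normal reference and 2.776 × 11.67 = 32.4 points on 4 df. The wider interval is the one that six schools can support.
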